### 10.3.1. Overall

An overall summary of AEs will show the number and percentage of patients (and the corresponding number of AEs) for infusional and noninfusional AEs and overall:

- any AEs
- any TEAEs
- any TEAEs by intensity
- any drug related TEAEs
- any serious TEAE
- any serious drug related TEAE
- any TEAEs leading to study drug infusion interruption / dose missed

This document is confidential.

- any TEAEs leading to study discontinuation / withdrawal
- any TEAEs leading to death

This table will be repeated by dosage interval (21- or 28-day) and by age category.

**Infusional AEs:**

Separate overall summaries of the infusional AEs will show the number and percentage of patients (and the corresponding number of AEs) who report during infusion or within 1, 24 or 72 hours after the end of infusion

- any infusional AEs,
- any nonserious infusional AEs,
- any related infusional AEs,
- any serious infusional AEs,
- any infusional AEs by intensity

The information will be presented overall and for each infusion.

This table will be repeated by dosage interval (21- or 28-day) and by age category.

Listings will be generated on the SAF for

- any AEs
- any drug related AEs
- any AEs leading to study discontinuation
- any serious AEs
- any fatal AEs
- any infusional AEs

10.3.2. By SOC/PT

An AE summary displaying SOC and PT will be presented for infusional and noninfusional AEs and overall:

- any TEAEs
- any severe TEAEs
- any drug related TEAEs
- any TEAEs leading to study discontinuation
- any serious TEAEs
- any serious drug related TEAEs
- any serious TEAEs leading to study discontinuation
- any fatal TEAEs

In addition, infusional AEs will be summarized by SOC and PT stratified by within 1, 24 or 72 hours after the end of infusion.

10.3.3. Relationship between infusional related AEs and speed of infusion

A 2-way table will summarize the frequency and proportion of infusion related AE by speed of infusion which will be grouped into different cohorts. This table will be produced overall and by the number of infusional related AE experienced per patient (e.g., 1 event experienced, 2 events experienced, 3+ events experienced).

This document is confidential.

#### 10.4. Laboratory Evaluations

Blood chemistry, hematology, urinalysis, IgG levels, IgG subclasses and specific antibodies samples, intravascular hemolysis testing and PK blood sampling will be analyzed at a central laboratory. Direct Coombs and urine hemosiderin can be tested either centrally or at site level. The pregnancy test on urine will be performed locally at each site. This section describes the statistical analyses for blood chemistry, hematology and urinalysis. The statistical analyses for the rest of the laboratory evaluations are described in relevant [Sections 8.2.1 – 8.2.6, 9.2 and 10.7](#). Please refer also to [Table 1.1](#) and [Table 1.2](#) for the timepoints for the collection of the specimen for the laboratory tests.

The tests listed below will be performed at screening visit, at each visit before the infusion, and at the study termination visit (week 51/52):

- Blood profile:  
hemoglobin, hematocrit, RBC count, WBC count with formula, number of platelets;
- Blood chemistry profile:  
total bilirubin, creatinine, blood urea nitrogen, ALT, AST, alkaline phosphatase, lactate dehydrogenase, glucose, sodium, potassium, chloride, and calcium;
- Urinalysis (qualitative and quantitative/semi-quantitative):  
bilirubin, pH, protein, blood, nitrite, specific gravity, leukocyte esterase, RBCs, WBCs.

These safety laboratory assessments will be categorized with respect to the central laboratory reference ranges as normal/abnormal. Abnormal values will be further classified with respect to clinical relevance: not clinically significant (NCS) or clinically significant (CS). Changes over time will be described by means of “shift-tables”, comparing the post-baseline values versus baseline value. Definition of baseline is given within [Section 6.2.2](#). Absolute change and relative change from baseline are defined in 6.2.3 and 6.2.4, respectively.

The raw data will be listed. Values below or above the reference values in the data listings will be flagged. All laboratory values will be converted into standard units for presentation reasons.

The pregnancy test on urine (for patients of childbearing age) will be also performed at the screening visit. All data will be listed.

#### 10.5. Vital Signs

The vital signs, including blood pressure, heart rate and temperature will be collected at each visit (including screening and study termination visit) and recorded in the eCRF.

Temperature method should be consistent throughout the study for any given patient.

All post-screening vital sign measurements will have an allowable window of  $\pm 5$  minutes. For each infusion, vital signs will be measured at rest at the following time points:

- 10 to 15 min pre-infusion
- After start of infusion: 5 minutes before each increase of the infusion rate
- 30 minutes after reaching the maximum infusion rate; every 60 minutes thereafter
- Immediately after completion of the infusion

The following information will be summarized for each scheduled visit:

- Actual value of the parameter

This document is confidential.

- Change from baseline of the parameter
- Relative change from baseline for parameter

Definition of baseline is given within [Section 6.2.2](#).

All available information will be listed.

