Rarely, Ig therapy may cause a sudden fall in blood pressure and, in isolated cases, anaphylactic shock, even when the patient has shown no hypersensitivity to previous administration.

Cases of reversible aseptic meningitis (Schroeder HW, 2012), and rare cases of transient cutaneous reactions (including cutaneous lupus erythematosus – frequency unknown) have been observed with human normal Ig. Reversible hemolytic reactions have been observed in patients, especially those with blood groups A, B, and AB. Rarely, haemolytic anemia requiring transfusion may develop after high dose IVIg treatment. A specific test for early detection of hemolysis will be performed during this clinical trial (see Section 8.2.3, Clinical Laboratory Analysis). The appearance of Coombs positivity after infusion of the study IVIGs occurred in few clinical trials. The proportion of patients that became Coombs-positive after infusion varied from 8.5 to 47%. However, none of the patients in any of earlier trials developed evidence of hemolysis or anemia (Schroeder HW, 2012).

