#### 6.2.2. Baseline

For purpose of the analysis, the baseline value is defined as the last nonmissing valid observation before the first infusion. In most cases this will be the Day 1 pre-dose value. However, if the Day 1 pre-dose value is missing or was obtained after the first infusion of study drug is administered, then the most recent value obtained prior to the initiation of study drug will serve as the baseline measurement and may be measured at an unscheduled visit.

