#### 6.2.3. Absolute Change from Baseline

Absolute change from baseline:

Absolute change = Post-baseline value – Value at baseline

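### SAP 10.5 plans no change in vital signs from each infusion's own pre-infusion reading, and does not say which time points will be tabulated

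*SAP*

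**What the plan says.** SAP 10.5 and Protocol 8.2.1 set the same measurement schedule for each infusion. There is a reading 10 to 15 minutes before the start, then "After start of infusion: 5 minutes before each increase of the infusion rate", then one half an hour after the maximum rate is reached, hourly readings from there, and one at the end.

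The analysis text in SAP 10.5 is short. "The following information will be summarized for each scheduled visit", followed by three items: the actual value, "Change from baseline of the parameter", and the relative change. For the reference value it says "Definition of baseline is given within" Section 6.2.2. There, "the baseline value is defined as the last nonmissing valid observation before the first infusion", and "In most cases this will be the Day 1 pre-dose value". SAP 6.2.3 gives the formula: "Absolute change = Post-baseline value – Value at baseline". SAP 6.4 adds that visits are summarised by nominal visit.

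These summaries serve safety endpoint 6 (SAP 4.5, Protocol 10.4.3), which covers changes in vital signs together with physical examination and laboratory tests. SAP 10.5, Protocol 8.2.1 and Protocol 10.4.3 define no second reference value and no change within a visit. All values are to be listed.

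**The concern.** Repeated readings around rate increases tell the reader about the infusion when they are compared with that session's starting value. The plan collects that value at every infusion but does not use it as a reference. The planned reference is one reading that is up to 48 weeks old by the last infusion.

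The protocol gives reasons to look at later infusions as well as the first. Section 2.3 notes "Rarely, Ig therapy may cause a sudden fall in blood pressure" and, in isolated cases, anaphylactic shock, even in patients without hypersensitivity at an earlier administration. It also says that higher infusion speed might matter for the safety profile. Under Protocol 7.1.1, infusions after the first start at 2 rather than 1 mg/kg/min and step up every 15 rather than every 30 minutes. These later infusions are the ones for which the planned baseline is another day's reading.

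At stake is whether the safety tables show, patient by patient, what happens to vital signs during an infusion, or show that mixed with whatever has changed since Day 1.

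**Working it through.** The documents state no figure on this point, so there is none to reproduce. The check follows the definitions and then illustrates their consequence.

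**Step 1: how many infusions have another day's reading as baseline.** The schedules have 13 infusions (28-day) and 17 (21-day). The baseline is normally that infusion's own pre-infusion reading only at infusion 1. That leaves 13 − 1 = 12 of 13 (92.3%) and 17 − 1 = 16 of 17 (94.1%).

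**Step 2: what the change contains.** For a during- or post-infusion reading at infusion *k*:

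(during *k* − Day 1 pre) = (pre *k* − Day 1 pre) + (during *k* − pre *k*)

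The first term on the right is drift since Day 1. The second is the change during the infusion. The planned change is their sum for each patient.

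**Step 3: what can be recovered.** If the same patients contribute at both time points:

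mean(during *k* − Day 1 pre) − mean(pre *k* − Day 1 pre) = mean(during *k* − pre *k*)

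The shared baseline cancels, so the mean infusion effect can be obtained free of drift. The standard deviation, minimum and maximum of the within-visit change cannot be obtained from two such summary rows.

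**Step 4: the two readings of SAP 10.5.** Counting the starting rates and steps in SAP 3.8, a first infusion that goes up to the maximum rate has 1 pre-infusion + 4 rate increases + 1 after maximum + 1 at the end = 7 time points. A later one has 1 + 3 + 1 + 1 = 6. Hourly readings are additional.

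- If these are all tabulated, Steps 2 and 3 apply at the 12 or 16 infusions in Step 1.
- If one value per visit is tabulated, drift does not contaminate an infusion-time change, because none is presented.

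On neither reading does the plan give a per-patient within-infusion change after infusion 1.

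**Step 5: illustration of the spread, on assumed values.** The documents give no standard deviations. Assume for systolic pressure a between-visit SD *b* of 5 to 12 mmHg and a within-session SD *w* of 5 to 8 mmHg, with independent deviations and an infusion effect that is the same for all patients.

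SD of change from Day 1 = √(2*b*² + 2*w*²)

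SD of change from own pre-infusion value = √(2*w*²)

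| *b* | *w* | From Day 1 | From own value | Ratio |
|---|---|---|---|---|
| 5 | 5 | 10.0 | 7.1 | 1.41 |
| 5 | 8 | 13.3 | 11.3 | 1.18 |
| 8 | 5 | 13.3 | 7.1 | 1.89 |
| 8 | 8 | 16.0 | 11.3 | 1.41 |
| 12 | 5 | 18.4 | 7.1 | 2.60 |
| 12 | 8 | 20.4 | 11.3 | 1.80 |

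**Step 6: illustration of the shift for one patient.** Take an assumed infusion fall of 10 mmHg. If resting pressure has risen 10 mmHg since Day 1, the planned change is +10 − 10 = 0. If it has fallen 10 mmHg, the planned change is −10 − 10 = −20. Against the visit's own pre-infusion value it is −10 in both cases.

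**The case against.** The strongest reply is that SAP 10.5 does not say infusion-time readings enter the change table. It speaks of scheduled visits, and the table shells that would settle the matter are not part of the documents. If only the pre-infusion value is tabulated, change from Day 1 is a sensible summary. A reader might infer that 12 of 13, or 16 of 17, infusions will be analysed against a wrong reference. The text does not support that as a fact; it holds only if during- and post-infusion readings are tabulated.

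A reader might also infer that the table could not show whether infusions change vital signs. That goes too far. If the time points are tabulated, the mean within-visit change follows from Step 3. What is lost is the spread and the individual extremes.

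Other routes exist for important reactions. Infusional adverse events are tabulated within 1, 24 and 72 hours and for each infusion (SAP 10.3.1), by system organ class and preferred term (10.3.2) and by infusion speed (10.3.3). Rate decreases due to adverse events are counted, and the proportion of infusions with a temporally associated event has a 0.4 criterion (10.1.2). Hypersensitivity, including anaphylaxis with blood pressure criteria, is an event of interest (Protocol 8.2.5). These capture what is reported as an adverse event. SAP 10.6 says that clinically significant abnormal examination findings after screening become adverse events; SAP 10.5 has no matching rule for vital signs. Falls not reported as events are the remaining gap.

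Finally, a single pre-treatment baseline is used consistently for laboratory values, vital signs and weight, and endpoint 6 does not define its change as pre- to during-infusion. So the plan does not contradict itself. It omits the comparison that its own measurement schedule makes possible.

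**Conclusion.** The point holds in limited form. SAP 10.5 leaves the tabulated time points unnamed and plans no change from the same visit's pre-infusion value, so no per-patient within-infusion change is produced after infusion 1. If infusion-time readings are tabulated, 12 of 13 or 16 of 17 infusions carry a change in which drift and infusion effect are combined for each patient. If they are not, that change is absent from the summaries.

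The counts and the decomposition follow from the documents. The 1.2- to 2.6-fold ratio and the 10 mmHg example rest on assumed values and are illustrations only; the size of any real drift is unknown. The direction under the model in Step 5 needs no particular value: any between-visit variation widens the spread.

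The consequence is small. SAP section 10 describes the safety results as descriptive, and vital signs carry no test or decision rule. The primary efficacy analysis and the 0.4 criterion are untouched. No data are lost, since all values are listed. With 40 evaluable patients, though, completed schedules would mean 40 × 13 = 520 to 40 × 17 = 680 infusions to work through by hand. This is a low-cost improvement to a safety summary.

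**What to change.** In SAP 10.5:

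1. Name the time points to be tabulated at each infusion.
2. For during- and post-infusion readings, summarise change from that infusion's own reading taken 10 to 15 minutes before the start, by time point.
3. Add the largest fall and the largest rise per infusion, on the same reference.
4. Keep change from the Day 1 baseline for the pre-infusion readings, where it describes drift over the study.

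The readings needed are already scheduled, so nothing changes for patients or sites. The cost is SAP wording, programming, and one or two additional tables.

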### **10.6. Physical Examination**

A physical examination will be performed at screening, at each visit before the infusion, and at the study termination visit. The general physical examination will include an evaluation of all body systems, as per normal standard of care at each site. Body weight measurement will be collected at each visit for pediatric patients and every 12 weeks (weeks 12, 24, 36, and 48) for adults.

For physical examination at screening, the number and percentage of patients with assessments of normal, abnormal or Not Done will be displayed in a summary table for each body system.

At the post-screening visits any abnormal, clinically significant findings are recorded as AEs. Therefore, abnormal findings of physical examination at these visits will be analyzed through the AE analysis.

For body weight, absolute values, changes from baseline and relative change from baseline will be presented for each scheduled study visit.

Definition of baseline is given within [Section 6.2.2](#). Absolute change and relative change from baseline are defined in 6.2.3 and 6.2.4, respectively.

All available information will be listed.

### **10.7. Intravascular hemolysis**

Intravascular hemolysis testing will be performed at the screening visit, after the first study infusion, after the 5th infusion for the 28-day infusion schedule or the 7th infusion for the 21-day infusion schedule, and at the study termination visit (week 51/52). Direct Coombs, serum haptoglobin, plasma-free hemoglobin, and urine hemosiderin tests will be performed. All blood samples related to intravascular hemolysis testing and Direct Coombs assessment will be analyzed at a central laboratory.

If a Direct Coombs test is positive, the test and serum haptoglobin, plasma-free hemoglobin, and urine hemosiderin tests must be repeated immediately after the initial positive results.

Intravascular hemolysis laboratory assessments (Coombs' test, serum haptoglobin, plasma-free hemoglobin, and urine hemosiderin) will be summarized by the number and percentage of patients with the given results at each scheduled visit. In case of positive Coombs' test results, further evaluations and/or time points will be included in the summaries. In case of intravascular hemolysis (drop in hemoglobin level by  $\geq 2.0$  g/dL and drop in serum haptoglobin to below the lower limit of normal and a rise in serum lactate dehydrogenase compared to the screening level), summaries will be presented for those patients meeting the conditions.

All information will be listed.

This document is confidential.

## 11. Interim Analyses

An interim PK analysis is planned after at least 20 patients will complete intense PK sampling before and after infusion 5 for 28 days schedule or infusion 7 for 21 days schedule. An interim PK report will be produced by the study PK scientist.

This document is confidential.

## 12. Changes from Analysis Planned in Protocol

Not applicable

This document is confidential.

## 14. Index of Tables

Please refer to the table shells.

This document is confidential.

## 15. Index of Figures

Please refer to the figure shells.

This document is confidential.

## 16. Index of Listings

Please refer to the listing shells.

This document is confidential.

